1 BACKGROUND AND RATIONALE

1.1 Background

Placebo is key in modern clinical practice, whereby it is widely used as control experiment in multiple trials. The neurobiological basis of placebo analgesia has been studied for over 40 years, since Levine at al. showed that the opiate antagonist naloxone could annul placebo analgesia after wisdom tooth extraction (Levine, 1978). More recent studies suggest that placebos can alter the experience of pain. For example, a recent study using functional magnetic resonance imaging (fMRI), found that placebo analgesia was related to decreased brain activity in pain-sensitive brain region (Wager TD, 2004). At the genomic level, it has also been shown that placebo analgesia might be objectively quantifiable (Hall KT, 2015). The literature addressing the question of placebo effects at the metabolomics level is very limited. However, the few studies addressing this, suggest a measurable, but not overwhelming effect (Kaddurah-Daouk R. B., 2013) (Kaddurah-Daouk R. B., 2011).

1.2 Rationale

Understanding the biological mechanisms of the placebo effects have a great and overarching impact into the broad field of clinical interventions. Amongst others, placebo effects tend to obscure efficacy of drugs. Any new tool to reduce this unwanted data variability, would benefit clinical trials as well as clinical practice and patient care. Furthermore, it may also reduce patient's exposure to drugs they might not need, henceforward reducing drug side-effects in overall population. Defining who might respond to placebo and how this happens biologically is of great importance as those who are very likely to respond to placebo could be excluded from clinical trials to increase the chances for seeing a drug-specific effect.

The literature suggests that placebo effects induce specific metabolic alterations, however the body of evidence is rather limited. This pilot study will provide additional insights into this very limited studied subject by addressing the question of whether placebo effects induces any measurable changes at the metabolic level. Because exhaled breath contains relevant metabolic information easily accessible, we will exploit this feature by interrogating the breath metabolome before and after the administration of a placebo in an established experimental pain procedure in healthy subjects.

2 STUDY OBJECTIVES AND DESIGN

3.1 Hypothesis and primary objective

Our hypothesis is that placebo effects exists, and that they modulate certain metabolic pathways. We will test this hypothesis by interrogating the exhaled breath metabolome while using an objective method of measurement for placebo effects in pain analgesia

(i.e. Cold Pressor Test; CPT). CPT reactions can be measured objectively by blood pressure spikes as well as changes in continuous heart rate monitoring. Those values have proven to be reliable in numerous studies and the model is ideal for measuring reduction of pain by various pharmaceuticals (Modir, 2010).

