3.2 Primary and secondary endpoints

Primary endpoint

The variable of primary interest is the variation of signal intensity of mass-to-charge ratio (m/z) of exhaled metabolites across the conducted CPT pain analgesia-placebo effects trial.

Secondary endpoints

Differentially exhaled metabolites across the pain vs. no-pain measurements. Exhaled metabolites for differences between placebo responders and non-responders. Exhaled metabolites association with blood pressure and heart rate.

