The participant receives an explanation how this study will work in terms of exhalation maneuvers, CPT and 'medication' (Placebo NaCl Nasal spray) and signs IC 1 if this is the first visit. The participant will then be connected to a patient monitor for continuous tracking of heart rate and blood pressure. The procedure is the same as in Visit A with the exception that participants will be told and read about the 'pain medication' (Appendix 3, the goal here is to enhance Placebo effects, Appendix 7: script of what the participants will be told about the medication), and that thereafter participants will self-administer a nasal spray, which is in fact a placebo nasal spray containing NaCl solution. Then, the CPT according to the 'CPT Guide' is performed (for details, see below). This takes around 5min. Directly after the CPT, the proband executes first post-pain exhalations set. Probands then rest 15min and executes the second post-pain exhalations set. In case this is the second visit, probands are debriefed and sign the IC 2. At all times, a medical doctor will be available in the UKBB premises in case the participant requires medical assistance.

VISIT B (CPT+ PLACEBO)

[figure not shown]

Figure 2. Schematic flowchart and process description of the study visit B

Cold Pressor Test (CPT)

The CPT is a widely used experimental technique for human pain induction, involving immersion of the hand or forearm in cold water. First documented as a test of cardiovascular reactivity (Hines & Brown, 1936), its application in investigation of pain perception, mechanisms, and treatment is due to a gradually mounting painful sensation of mild to moderate intensity. As water temperatures used are within the range considered noxious (below 15°C), nociceptors (pain receptors) are activated and transmit an aversive signal to the Central Nervous System (CNS). Like other pain inductions, the cold pressor allows fast and precisely controlled evaluations not possible in a clinical context (L.A., 2013). CPT is safely performed on thousands of participants (largest cohort up to date with 10'486 adult participants (Johansen, 2014)) including children every year worldwide and is generally well tolerated (Birnie & Noel, 2010). The principle is simple and safe, it is even employed in online self-administration research where 1876 participants self-administered CPT from their home (McIntyre MH, 2020).

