Apparatus for the task is a tank of water of temperature of 2 °C (+-1 °C), with instruction to immerse the hand until too uncomfortable to continue. A maximum time limit per immersion of 3-5 min is applied. Quantitative measurement can then be made of pain threshold (point first perceived as painful) and tolerance time.

Figure 3. CPT Guide

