Appendix 1: Schedule of assessments

| Visit | 1 | 2 |
|---------------------------|--------|--------|
| Time | 60 min | 60 min |
| Oral information | + | + |
| IC 1 | + | |
| IC 2 | | + |
| Check inclusion-/ | + | |
| exclusion criteria | | |
| CPT | + | + |
| Self-Report Pain | + | + |
| Heart rate Monitoring | + | + |
| Blood Pressure Monitoring | + | + |
| Breath analysis | + | + |
| Placebo | | + |

(uploaded to BASEC system):

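### Responder endpoint: the protocol splits 20 people on an undesignated cold pressor response, and the blood-pressure spike it names is read under self-ended, unequal cold exposure

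*Protocol*

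**What the plan says.** Protocol 3.2 lists as a secondary endpoint "Exhaled metabolites for differences between placebo responders and non-responders". No section says what makes a responder. Three kinds of measurement could serve:

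- **Haemodynamic.** Section 3.1 describes the cold pressor test (CPT) as "using an objective method of measurement for placebo effects in pain analgesia" and adds "CPT reactions can be measured objectively by blood pressure spikes as well as changes in continuous heart rate monitoring".
- **Behavioural.** The CPT text in 3.4 says "Quantitative measurement can then be made of pain threshold (point first perceived as painful) and tolerance time".
- **Self-report.** Appendix 1 lists "Self-Report Pain" at both visits. It has rows for heart rate and blood pressure but none for threshold, tolerance or immersion time.

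The same CPT text sets the exposure: the participant works "with instruction to immerse the hand until too uncomfortable to continue", and "A maximum time limit per immersion of 3-5 min is applied". Section 3.4 attributes the use of the test in pain research to a sensation that builds up: its application is "due to a gradually mounting painful sensation of mild to moderate intensity".

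**The concern.** A responder definition and its cut-off could wait for a statistical analysis plan. Two things, however, are already set in the protocol.

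First, 3.2 specifies a two-group comparison. With 20 people, dichotomising the response discards information, and membership of the groups depends heavily on the measure chosen.

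Second, 3.1 puts forward the blood-pressure spike as an objective reading of the placebo effect, while 3.4 lets the participant end the immersion. Someone with real analgesia may keep the hand in longer at Visit B and so receive more cold. A peak reading then mixes two opposing influences: less reaction per unit of exposure, and more exposure.

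The rationale (1.2) stresses identifying who responds to placebo, so this endpoint carries weight in how the pilot will be read. The false discovery rate procedure in 5.1 deals with multiple testing; nothing there covers a choice among response measures made after the data are seen.

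**Working it through.** The protocol gives no figure to reproduce: 5.1 bases the 20 participants on a rule of thumb, and no correlation, pressor size or immersion time is stated. Everything below except n = 20 is an assumed input for illustration.

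**1. Agreement between two measures.** Suppose a responder is anyone above the median on a measure, and two measures are bivariate normal with correlation r. The share classified differently is arccos(r)/π.

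| r (assumed) | Share | Of 20 people |
|---|---|---|
| 0.7 | 25.3% | 5.1 |
| 0.5 | 33.3% | 6.7 |
| 0.3 | 40.3% | 8.1 |
| 0 | 50.0% | 10.0 |

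This holds for any two imperfectly correlated measures. It shows only that the choice of measure matters at this sample size.

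**2. Cost of splitting.** For normal data, a median split multiplies a correlation by √(2/π) = 0.798, so 0.5 becomes 0.40. Simulating one metabolite, n = 20, two-sided alpha 0.05 and r = 0.5 gives power of about 0.64 with the continuous response and about 0.41 with the split. Neither figure allows for multiplicity across metabolites.

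**3. Direction of the spike, simple model.** Assume the pressor rise is proportional to immersion time, and placebo lowers the slope by a fraction c. The ratio of the Visit B peak to the Visit A peak is (1 − c) × (t_B / t_A).

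- c = 0.15, immersion from 1.0 to 1.5 min: 0.85 × 1.5 = 1.275. The spike is larger under placebo despite analgesia.
- c = 0.15, immersion from 1.0 to 1.1 min: 0.85 × 1.1 = 0.935. The spike is smaller, so spike and tolerance time agree.
- Break-even at c = 0.15 is t_B / t_A = 1/0.85 = 1.18.

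**4. Direction of the spike, levelling-off model.** Assumed inputs:

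- Rise = 20 mmHg × (1 − exp(−t/τ)), with τ = 30, 60 or 90 s.
- Median immersion 60 s (lognormal, log-SD 0.7), capped at 180 or 300 s.
- Immersion 25%, 50% or 100% longer under placebo.
- True reduction of 10% or 20% at equal exposure.
- Independent noise with SD 5 mmHg per visit.

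That is 3 × 2 × 3 × 2 = 36 scenarios, each with a true placebo effect.

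| | Peak spike | Common immersion time |
|---|---|---|
| Mean Visit B − Visit A | −2.5 to +2.7 mmHg | −3.3 to −1.0 mmHg |
| Share showing a smaller value at Visit B | 35% to 64% | 55% to 68% |
| Scenarios with the mean in the wrong direction | 16 of 36 | 0 of 36 |

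Of the 16 reversals, 10 need immersion to double and 12 have the smaller (10%) reduction. None occurs at a 20% reduction with immersion 25% to 50% longer.

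Noise also matters. The difference between visits has SD 5 × √2 = 7.1 mmHg, so a true mean change of −1.0 to −3.3 mmHg gives the right sign in only about 56% to 68% of people even at matched exposure. This is a further reason not to label individuals.

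**5. Self-report at withdrawal.** If participants stop at a similar self-chosen level of discomfort at both visits, a rating made at that moment is similar at both, and analgesia appears as longer immersion instead. Appendix 1 gives no rating time, so whether this applies is unknown.

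**The case against.** The best counter-argument is that nothing here is a contradiction. Sections 3.1 and 3.4 say only that these measurements can be made, Appendix 1 merely lists one, and neither 3.1 nor the CPT text mentions responders. Collecting physiological, behavioural and self-report data on one stimulus is ordinary practice, and the designation may sit in an analysis plan or in appendices not supplied. This stands. A reader might infer three conflicting rules for who is a responder, but the documents show three candidates with none designated, and a missing designation alone would not be a finding.

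A reader might also infer that the spike in fact pushes true responders into the non-responder group. The documents do not support that. They say that pain mounts during immersion, not that blood pressure does, and every magnitude above is assumed. Opposite readings are possible, not shown.

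Nor can one say that the responder endpoint duplicates the third secondary endpoint (metabolites against blood pressure and heart rate). That follows only if haemodynamics define response, which 3.2 never says.

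Replacing the spike with self-reported pain as the sole measure is no ready answer either, for the reason in step 5.

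What the objection does not remove is the two-group form fixed in 3.2, and the unequal exposure that self-ended immersion builds into any peak reading.

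**Conclusion.** The point holds in a limited form. The protocol offers three candidate response measures, ties none to the responder endpoint, and commits to splitting 20 people. Under self-ended immersion, the measure 3.1 presents as objective is not compared at equal exposure.

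The loss from splitting needs no physiological assumption: power of about 0.64 against about 0.41 at an assumed correlation of 0.5. That the spike can understate or reverse a real effect rests on the unstated assumption that the pressor response grows with exposure. Where that holds, the result depends on how much longer immersion lasts under placebo and on the shape of the rise.

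The consequence is confined to secondary endpoints. The primary comparison of CPT with CPT plus placebo in 5.1 uses no responder status.

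**What to change.** - **3.2:** Designate one response measure before data are seen, defined as the within-person Visit B minus Visit A difference. Relate it to metabolites as a continuous variable in place of the responder and non-responder groups.
- **CPT text and Appendix 1:** Record immersion time at both visits, the limit applied to each immersion (the text gives a range), and when pain is rated.
- **3.1:** Compare blood pressure and heart rate over the immersion time common to a participant's two visits, that is up to the end of the shorter one, instead of by peak. Do the same for pain if it is rated during immersion.
- **Tolerance time:** Treat it as censored at the limit. People who reach the limit at both visits have tied times and cannot be classified by it.
- Reconcile 3.1, 3.2, the CPT text and Appendix 1 accordingly.

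The cost is wording, one extra recorded time per visit, and some additional processing of heart-rate and blood-pressure tracks that 3.4 already calls continuous. The simple two-group presentation is lost. The immersion procedure itself need not change.

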3.2 Primary and secondary endpoints

Primary endpoint

The variable of primary interest is the variation of signal intensity of mass-to-charge ratio (m/z) of exhaled metabolites across the conducted CPT pain analgesia-placebo effects trial.

Secondary endpoints

Differentially exhaled metabolites across the pain vs. no-pain measurements. Exhaled metabolites for differences between placebo responders and non-responders. Exhaled metabolites association with blood pressure and heart rate.

3.3 Study design

Single center; national, implemented at the University Children's Hospital Basel (UKBB). Randomized Crossover design; Pilot Study.

3.4. Study intervention

Visit A (CPT, 60 min)

The participant receives an explanation how this study will work in terms of exhalation maneuvers, medication and CPT and signs informed consent (IC) 1 if this is the first visit. The participant will then be connected to a patient monitor for continuous tracking of heart rate and blood pressure. An exhalation set typically contains six replicate exhalations in positive and negative ion mode. The method is highly standardized, as described in (Singh, Tancev et al. 2019), whereby exhalation maneuvers are controlled by a mass flow controller and guided by CO₂ exhalation. Typical coefficients of variation for such replicate measurements are in the order of 7%. In total, this process takes around seven minutes. First, two baseline exhalations are performed. Then, the CPT is performed according to the 'CPT Guide' (for details, see below Figure 3). This takes around 5min. Directly after the CPT, the proband executes first post-pain exhalations set. Probands then rest 15min and executes the second post-pain exhalations set. In case this is the second visit, probands receive 100CHF. At all times, a medical doctor will be available inside the UKBB premises in case the participant requires medical assistance.

[figure not shown]

Figure 1. Schematic flowchart and process description of the study visit A

Visit B (CPT+Placebo, 60 min)

The participant receives an explanation how this study will work in terms of exhalation maneuvers, CPT and 'medication' (Placebo NaCl Nasal spray) and signs IC 1 if this is the first visit. The participant will then be connected to a patient monitor for continuous tracking of heart rate and blood pressure. The procedure is the same as in Visit A with the exception that participants will be told and read about the 'pain medication' (Appendix 3, the goal here is to enhance Placebo effects, Appendix 7: script of what the participants will be told about the medication), and that thereafter participants will self-administer a nasal spray, which is in fact a placebo nasal spray containing NaCl solution. Then, the CPT according to the 'CPT Guide' is performed (for details, see below). This takes around 5min. Directly after the CPT, the proband executes first post-pain exhalations set. Probands then rest 15min and executes the second post-pain exhalations set. In case this is the second visit, probands are debriefed and sign the IC 2. At all times, a medical doctor will be available in the UKBB premises in case the participant requires medical assistance.

VISIT B (CPT+ PLACEBO)

[figure not shown]

Figure 2. Schematic flowchart and process description of the study visit B

Cold Pressor Test (CPT)

The CPT is a widely used experimental technique for human pain induction, involving immersion of the hand or forearm in cold water. First documented as a test of cardiovascular reactivity (Hines & Brown, 1936), its application in investigation of pain perception, mechanisms, and treatment is due to a gradually mounting painful sensation of mild to moderate intensity. As water temperatures used are within the range considered noxious (below 15°C), nociceptors (pain receptors) are activated and transmit an aversive signal to the Central Nervous System (CNS). Like other pain inductions, the cold pressor allows fast and precisely controlled evaluations not possible in a clinical context (L.A., 2013). CPT is safely performed on thousands of participants (largest cohort up to date with 10'486 adult participants (Johansen, 2014)) including children every year worldwide and is generally well tolerated (Birnie & Noel, 2010). The principle is simple and safe, it is even employed in online self-administration research where 1876 participants self-administered CPT from their home (McIntyre MH, 2020).

Apparatus for the task is a tank of water of temperature of 2 °C (+-1 °C), with instruction to immerse the hand until too uncomfortable to continue. A maximum time limit per immersion of 3-5 min is applied. Quantitative measurement can then be made of pain threshold (point first perceived as painful) and tolerance time.

Figure 3. CPT Guide

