4 STATISTICS AND METHODOLOGY

5.1. Statistical analysis plan and sample size calculation

This is a pilot study and no literature has been found on the topic of placebo and metabolomics that may allow for a reasonable sample size estimation. Thus, we employ a rule of thumb approach based on our experiences in previous metabolomics studies (Pablo Sinues, 2013). (Pablo Sinues Tarokh L, 2014)

All 20 participants will undergo two study visits. The order in which they will receive differs, with participants being randomly split into two groups via matlab randi function: 10 participants first CPT + placebo and then CPT, and 10 participants vice versa. Null and alternative hypotheses are formulated as follows:

- Null hypothesis: the mean difference concentration (i.e. signal intensity as proxy) of exhaled metabolites is equal in CPT and in CPT+placebo ($\mu_{CPT} = \mu_{CPT+Placebo}$)
- Alternative hypothesis: the mean difference concentration (i.e. signal intensity as proxy) of exhaled metabolites is significantly different in CPT and in CPT+ placebo ($\mu_{CPT} \neq \mu_{CPT+Placebo}$)

A two-way repeated measures ANOVA will be performed to evaluate the effect of different treatments (CPT and CPT + placebo) over time on exhaled metabolite abundance. False discovery rate for multiple testing will be taken care using established procedures (Storey, 2002). The preprocessing of the raw mass spectra and the statistical analysis will be implemented using MATLAB (MathWorks, Massachusetts, US).

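### Visit A has no step matching the spray, and apparently the script and reading, that precede the CPT at Visit B, so time from baseline to CPT differs with treatment in the primary contrast

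*Protocol*

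**What the plan says.** Protocol section 3.4 gives the order at Visit A: "First, two baseline exhalations are performed. Then, the CPT is performed according to the 'CPT Guide". No wait, reading or neutral task stands between the two steps.

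Visit B is defined by its differences from Visit A: "The procedure is the same as in Visit A with the exception that participants will be told and read about the 'pain medication". The stated purpose of that material is that "the goal here is to enhance Placebo effects". Then "thereafter participants will self-administer a nasal spray, which is in fact a placebo nasal spray containing NaCl solution", and the CPT follows. No duration is given for the script, the reading or the spray. From the CPT onward the two visits are worded alike: about 5 minutes of CPT, a first post-pain exhalation set, 15 minutes of rest and a second set.

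Section 1.2 says that breath is measured on both sides of giving the placebo, so the baseline comes before the spray.

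Section 5.1 sets the primary analysis: "A two-way repeated measures ANOVA will be performed to evaluate the effect of different treatments (CPT and CPT + placebo) over time". Order is randomised: "10 participants first CPT + placebo and then CPT, and 10 participants vice versa".

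**The concern.** In this crossover each participant is their own control, so the comparison is only as clean as the match between the two visits. As written, Visit B carries extra minutes between baseline and CPT, with some general reading and staff contact, and Visit A does not. Breath signals that change with time sitting at rest would have moved further by the CPT and the post-pain sets at Visit B, whether or not the placebo did anything.

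The analysis would show this as a treatment effect over time. A metabolite that merely drifts could be listed as placebo-responsive and carried into follow-up work, which matters for a pilot meant to show whether placebo leaves a measurable metabolic trace.

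**Working it through.** **Sequences side by side (section 3.4)**

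| Step | Visit A | Visit B |
|---|---|---|
| Baseline exhalations | yes | yes |
| Told and reads about the medication | no | yes, no duration stated |
| Nasal spray | no | yes, no duration stated |
| CPT | about 5 min | about 5 min |
| First post-pain set | about 7 min | about 7 min |
| Rest | 15 min | 15 min |
| Second post-pain set | about 7 min | about 7 min |

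That the spray follows the baseline rests on section 1.2. That the script and reading also follow it is the natural reading of section 3.4, but the text does not say so outright.

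**Why randomised order does not help.** For one feature, let τ be the placebo effect on change from baseline, δ the extra drift from the longer interval at Visit B, and π₁ and π₂ the period effects. The expected Visit B minus Visit A difference is:

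- Visit B first: τ + δ + (π₁ − π₂)
- Visit A first: τ + δ + (π₂ − π₁)

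With 10 participants per sequence the mean is τ + δ. The period terms cancel. The drift term stays, because it goes with the treatment and not with the period.

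**Why false discovery rate control does not help.** It limits chance findings among features with no difference between conditions. A feature with δ ≠ 0 has a real difference between the visits, but one not caused by the placebo.

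**Size.** The plan has no figure to reproduce: n = 20 is a rule of thumb without alpha, power, effect size or SD. The protocol also gives no drift, no length for the extra steps and no between-visit SD. As an illustration only, take a paired two-sided t test with n = 20 (19 df), τ = 0, and δ equal to d SDs of the paired difference. The noncentrality is d√20, and the critical value is 2.093 at 0.05.

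| d (assumed) | d√20 | Rejection probability at 0.05 | At an assumed 0.001 |
|---|---|---|---|
| 0.10 | 0.447 | 7.1% | 0.2% |
| 0.25 | 1.118 | 18.6% | 1.0% |
| 0.50 | 2.236 | 56.5% | 8.7% |

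The last column (critical value 3.883) stands in for a stricter per-feature threshold. The actual threshold under the planned procedure depends on the data.

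**Room in the visit.** If the baseline is one set of about 7 minutes, the timed steps take 7 + 5 + 7 + 15 + 7 = 41 minutes, leaving 60 − 41 = 19. If it is two sets, they take 14 + 5 + 7 + 15 + 7 = 48 minutes, leaving 12. Explanation, consent at a first visit and connection to the monitor must also fit into that remainder, and none has a stated duration. So the shared 60-minute label does not show that the pre-CPT intervals match, and the spare time is not established either.

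**The case against.** **The script is the intervention.** Its stated aim is to strengthen the placebo response, so expectation and attention raised by it belong to the CPT + placebo condition. A reader might count the whole difference in attention as contamination. The protocol does not support that. What remains is elapsed time and non-specific reading or contact time.

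**The order is partly inferred.** Section 3.4 never places the baseline relative to the reading. If the reading comes first, the unmatched interval shrinks to the spray. Figures 1 and 2 are not shown and could settle the order or show a wait at Visit A. This stands as a limit. Against it, the text presents the added steps as the exceptions to an otherwise identical procedure, and the spray must still fall between baseline and CPT.

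**The bias may be negligible.** This also stands. A reader might combine the 7% replicate coefficient of variation with a guessed drift and arrive at a high false-positive rate. That would not be sound: the 7% describes replicate exhalations only, leaves out biological variation between visits at least 24 hours apart, and says nothing about drift.

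**It is a pilot, and a no-treatment comparator is a legitimate choice.** Agreed. The point leaves the comparator in place and asks only for a matched interval, since section 5.1 still tests a formal hypothesis on this contrast.

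**A neutral wait before expected pain may itself alter arousal.** This is possible. Visit B also has a delay before the CPT, so a matched wait brings the visits closer, though not to identity.

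**Conclusion.** The point holds in limited form, as a low-cost improvement. As section 3.4 reads, the baseline-to-CPT interval and non-specific reading or contact time differ systematically with treatment. Any resting drift over that interval is inseparable from the placebo effect in the primary contrast. This rests on the baseline preceding the spray (section 1.2) and on the figures not shown adding no matching step.

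The direction and size of the bias are unknown. The rejection probabilities above show how sensitive 20 paired observations are to a shift of a given standardised size. They do not estimate a bias in this trial.

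A reader might infer that positive findings will be artefacts, or that clock times are not being recorded. Neither follows. No drift is documented, and the log file in Appendix 8, which may hold the times, is not visible.

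**What to change.** In section 3.4:

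1. State where the Visit B script and reading fall relative to the baseline exhalations.
2. Set one fixed interval from the last baseline exhalation to the CPT, the same at both visits.
3. Fill it at Visit A with a neutral text and a wait that together last as long as the Visit B steps in that interval. Use no spray at Visit A, so nothing about the deception is disclosed.
4. Use the clock times of the exhalation sets to confirm the match.
5. Word the conclusion as placebo spray with instructions versus no spray, because any physical effect of saline remains unseparated.

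The cost is a few more minutes at Visit A, a short neutral text and a small protocol amendment, with no extra participants or staff. Check that the visit still fits in 60 minutes, since explanation, consent and monitor connection are untimed.

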4.2 Recruitment, screening and informed consent procedure

Participants will be recruited from the University campus/Hospital of Basel by word of mouth, flyers and via advertisement on the homepage of the University of Basel and social media. A minimum of 24 hours between recruitment procedure and decision of participant to participation is given. Due to the study design, the participants cannot be informed about all aspects of the procedure before the start of the study. Therefore, at the first Visit (randomly A or B), the investigators will explain to each participant the nature of the study as described in IC 1 (see appendix 2). Further, the procedures involved will be explained, the expected duration, the potential risks and benefits and any discomfort they may entail. The participants then sign IC 1. IC 1 will be signed and dated by the investigator or his designee at the same time as the participant sign. No medical records will be screened for this study.

Participants will receive CHF 100 for their participation in both study visits. After maximum 6 months or in case of withdrawal, the participants will be debriefed about the true aim of the study and sign IC 2 (see appendix 2) which they will receive via post. A copy of the signed informed consents will be given to the study participant. The consent forms will be retained as part of the study records.

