4.3 Study procedures

The overall study duration will be: Recruitment start date: 01.10.2021, Study completion: 28.02.2023. The study comprises two visits (A and B) of 60 minutes each at the Breath Analysis laboratory of [name] (UKBB). The breath analysis platform consists of a commercially available ion source (FIT, Spain) coupled to a high-resolution mass spectrometer (Thermo Scientific, Bremen). The process is completely non-invasive as the participant just exhales through a commercially available disposable bacterial/viral filter coupled to the ion source.

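### Debriefing is not laid down consistently for the two visit orders, and same-day debriefing after Visit B may disclose the saline spray while others are still to be tested

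*Protocol*

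**What the plan says.** Section 3.4 closes its description of Visit B with: "In case this is the second visit, probands are debriefed and sign the IC 2". The matching sentence for Visit A is "In case this is the second visit, probands receive 100CHF", and nothing is said there about debriefing or IC 2.

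Section 4.2 gives a general provision without reference to visit order: "After maximum 6 months or in case of withdrawal, the participants will be debriefed about the true aim of the study and sign IC 2". It adds of IC 2, "which they will receive via post".

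The schedule in Appendix 1 marks IC 2 at visit 2. It also marks placebo at visit 2 only, although section 5.1 allocates "10 participants first CPT + placebo and then CPT, and 10 participants vice versa".

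Recruitment under section 4.2 is from one campus and hospital, "by word of mouth, flyers and via advertisement on the homepage of the University of Basel" and social media. The only dates are in section 4.3: "Recruitment start date: 01.10.2021, Study completion: 28.02.2023". Nothing in the protocol text ties debriefing to the last participant's completion or asks debriefed participants to keep the placebo to themselves.

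**The concern.** Staff cannot apply these provisions uniformly. For a participant who has Visit B first and Visit A second, section 3.4 gives no step, section 4.2 sends IC 2 by post at some time within 6 months, and Appendix 1, if taken to cover everyone, has it signed at visit 2. Section 7.1 names the hidden placebo as one of two main ethical considerations, so the moment of disclosure should not depend on which page is followed.

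There is also a statistical side. Visit B works only if the participant believes the spray is an analgesic; section 3.4 says the information given is meant to strengthen the placebo effect. Section 5.1 tests CPT against CPT plus placebo. A participant who has heard that the spray is saline contributes a weaker contrast, which pulls the estimate towards no difference. Debriefing half the participants on the day, in a study that recruits partly by word of mouth, opens a route for that.

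**Working it through.** **Step 1: the provisions side by side.**

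| Place | Visit B second (10 participants) | Visit A second (10 participants) |
|---|---|---|
| Section 3.4 | Debriefed on site, IC 2 signed | Payment only; debriefing not mentioned |
| Section 4.2 | Within 6 months or at withdrawal; IC 2 by post | The same |
| Appendix 1 | IC 2 at visit 2 | Order not depicted (placebo at visit 2 only) |

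A same-day debriefing falls inside a 6-month maximum, so sections 3.4 and 4.2 are compatible in timing. They differ in route (on site against post), and no place gives a complete rule for both sequences.

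**Step 2: the dates.** From 01.10.2021 to 28.02.2023 is 515 days, about 16.9 months. Six months (about 182.6 days) is 182.6/515 = 35% of that window. The window runs from recruitment start to study completion; the recruitment period itself is not given.

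**Step 3: how many could enrol after the first debriefing.** Assumptions, not in the protocol: 20 participants enrol at even spacing over R months, participant i (i = 0 to 19) at i × R/19, and the delay to debriefing counts from enrolment. Anyone with i × R/19 greater than the delay is called later.

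| Delay to first debriefing | R = 1 | R = 6 | R = 9 | R = 12 | R = 17 |
|---|---|---|---|---|---|
| 1 day (section 3.4, the minimum gap of 24 hours) | 19 | 19 | 19 | 19 | 19 |
| 2 weeks (section 3.4, longer gap) | 11 | 18 | 19 | 19 | 19 |
| Full 6 months (section 4.2) | 0 | 0 | 7 | 10 | 13 |

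The first two rows take the first participant to have Visit B second. If not, on-site debriefing starts somewhat later. With 10 of 20 in that sequence, the chance that none of the first 3 is in it is C(10,3)/C(20,3) = 120/1,140 = 10.5%, and for the first 5 it is C(10,5)/C(20,5) = 252/15,504 = 1.6%.

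**Step 4: what disclosure could cost.** Let L be the number of later participants and f the assumed share of them who lose the effect entirely. The mean effect is multiplied by 1 − f × L/20. With unchanged variance, the sample needed for the same precision relative to the effect is multiplied by 1/(1 − f × L/20)². With f = 20%, which is assumed:

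- L = 10: 1 − 0.2 × 10/20 = 0.90; 1/0.90² = 1.23
- L = 13: 1 − 0.2 × 13/20 = 0.87; 1/0.87² = 1.32
- L = 19: 1 − 0.2 × 19/20 = 0.81; 1/0.81² = 1.52

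The protocol has no figure to reproduce here. Its sample size is a rule of thumb, without a stated effect size or power.

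**The case against.** The strongest reply is that the text can be made to work: debrief on site when Visit B is last, otherwise by post within 6 months. Appendix 1 may simply depict the order with Visit A first, where it agrees with section 3.4. The closing sentences of the two visits look incomplete rather than rule-like: the Visit B sentence omits payment, yet section 4.2 pays everyone. The visit flowcharts are not shown and may fill the gaps. Much of this stands, and a reader who infers three mutually exclusive rules goes too far. But the workable reading has to be constructed: section 4.2 does not split by order, and Appendix 1 has no column for the order with Visit B first.

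On contamination, a reader might infer that disclosure will reach later participants, or that exposure lasts most of the study. The protocol does not support either. Word of mouth is one channel among several, no recruitment end date is given, and under the full 6-month delay nobody enrols later if recruitment takes 6 months or less. The consent forms, CRF and script are not shown and might contain a non-disclosure request or a question about belief.

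A reader might also apply the 20% to the whole sample, giving 0.80 and 1/0.80² = 1.56. That would require all 20 to be later, which cannot be: the first participant debriefed did not enrol after that debriefing.

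**Conclusion.** The inconsistency is established from the protocol text: route differs between sections 3.4 and 4.2, the sequence ending in Visit A has no step in section 3.4, and Appendix 1 does not represent the randomised orders. There is no conflict in timing, because the 6 months are a maximum.

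The threat to the placebo contrast is a conditional risk. Under section 3.4 it arises with almost any staggered enrolment; under the full delay of section 4.2 it arises only if recruitment exceeds 6 months. The illustrated loss, to 0.90 down to 0.81 of the effect, rests on an assumed 20% and even enrolment. It shows scale and is not a forecast. The point deserves correction because the repair is cheap, but it does not invalidate the design.

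**What to change.** Reconcile sections 3.4 and 4.2 and Appendix 1 into one debriefing rule that covers both sequences and states time and route:

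- Use the time section 4.2 already allows: hold debriefing until the last participant's second visit where that falls within 6 months, and state from when the 6 months count.
- Keep debriefing at withdrawal.
- Ask every participant debriefed before the last Visit B, including those who withdraw, not to disclose the placebo. This is the main safeguard if recruitment lasts longer than 6 months.
- Redraw Appendix 1 to show both visit orders.
- Optionally, add one question after each participant's last CPT on what they believed the spray was, and report it descriptively. Any analysis leaving out those who guessed placebo should be exploratory only: the guess is made after treatment and is related to response, so exclusion would favour finding an effect.

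Costs: the half with Visit A first would be told later than section 3.4 now provides, some posted IC 2 forms may not be returned, and the amendment may need Ethics Committee approval before implementation under section 6.6. No visit, participant or measurement procedure changes, apart from the optional question.
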